3.7.3 Nutritional status

Nutritional status will be evaluated by a registered dietician with the use of initial nutritional assessment and follow up nutritional assessment. Nutritional panel (Iron, Folate, B12, Vitamin D 25-Hydroxy, PTH, Magnesium, Phosphorus) will be performed every 3 months for the first year and then annually for 5 years.

3.7.4 Psychiatric Status

Psychiatric Status will be evaluated by child study center psychologist with the use of an interview, a child behavior checklist (parent and self-report, a standard screen for general psychopathology), a youth evaluation scale (parent and self-report, YES has been utilized with a particular educational weight loss program to assess readiness for treatment as well as screen for psychopathology), a three-factor eating questionnaire (to measure three dimensions of human eating behavior, 1) cognitive restraint of eating, 2) disinhibition, and 3) hunger), and a child depression inventory (a standard screen for depression). Status of quality of life will be evaluated objectively with a standardized SF-36 Health Survey.

3.7.5 Safety Evaluations

Mortality:

Thirty day mortality will be evaluated to monitor death, which may have been directly related to the intervention.

Esophageal dilation:

The long-term effects of gastric banding on esophageal motility are unknown. The risk of chronic esophageal dilatation with loss of peristalsis is theoretical and unproven. Annual post-operative esophagrams will be performed to monitor esophageal anatomy and band positioning. If necessary, esophageal manometry will be performed to evaluate for esophageal dysmotility if patient presents with dysphagia and abnormal esophagram indicating achalasia.

Nutritional deficiency:

Although there has been no known nutritional deficiency linked with gastric banding, there have been no long-term studies that measure biochemical markers of nutrition or evaluation of eating behavior. Potential nutritional deficiencies will be monitored with annual blood work and nutritional evaluations, as described.

3.7.6 Statistical Methods

Change in the primary efficacy endpoint, % EWL, will be evaluated by a linear modeling in which the covariance among repeated measures of weight loss from month 6 to month 60 is

modeled. SAS PROC MIXED will be used in which two covariance structures will be examined by means of a REPEATED statement: unstructured (UN) and autoregressive (AR(1)). AIC will be examined to determine the most suitable structure. In the case that AR(1) is selected, a RANDOM statement for Subject will be included in the model. The predictive variable of greatest interest in the model is time. % EWL is expected to increase after surgery, more quickly initially, and then more slowly. To test for this decelerating trend, Time will be log transformed. The residuals of the model will be examined, especially those relative to predicted weight loss over time to ensure that the model is not over or under predicting over the course of follow-up. Systematic departures of the residuals from the predicted time course may require adding a quadratic trend to the model or the choice of a different transformation for time. Covariates used in the model will include baseline weight (as measured by BMI).

The null hypothesis is that % EWL will remain unchanged (i.e., at zero) post surgery. The alternate hypothesis is that % EWL will be positive post surgery. An alpha of 0.05 will be used to determine if the null hypothesis is rejected. The form of the weight loss over time is not part of the hypothesis of the study, but instead is included to better understand the expected trend weight loss follows.

The secondary efficacy endpoint, BMI, will be tested using a model similar to that used to test % EWL. The covariance structure selected for the modeling of % EWL will be applied in the modeling of BMI. Similarly, the same transformation of time will be applied to this endpoint. Baseline BMI will not be included as a baseline covariate, but instead will be assigned a value of time 0 and will be included as an endpoint measure. The null hypothesis is that BMI will show no change from time of surgery. The alternate hypothesis is that BMI will decrease after surgery.

The secondary efficacy endpoint of change in co-morbidities will be examined by McNemar tests. The null hypothesis is that there is no change in each co-morbidity post surgery. The alternate hypothesis is that there will be a change in each co-morbidity.

The secondary efficacy endpoint of quality of life change, as measured by the SF36 scale, will be examined by testing the mean change against the null hypothesis of zero (no change) by means of a paired t-test. The alternate hypothesis is that improvements will be seen between pre and post surgery in SF36 scale scores. A further analysis will examine whether change in SF36 scale scores is correlated with amount of weight lost.

The secondary efficacy endpoint of depression change, as measured by the child depression inventory, child behavior checklist, and youth evaluation scale, will be examined by testing the mean change against the null hypothesis of zero (no change) by means of a paired t-test. The alternate hypothesis is that improvements will be seen between pre and post surgery in depression inventory scores. A further analysis will examine whether change in depression is correlated with amount of weight lost.

Descriptive statistics will be provided for secondary variables such as nutrition status, psychiatric evaluations, etc.

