3.4.5 Follow-Up Visits

3.4.5.1 Scheduled Visits

Study data will be collected at 1-2 week, 6 weeks, 3 months, 6 months, 9 months, 12 months, and every 6 months thereafter for a total of five years. Subjects will be weighed and given a physical examination. Parents and subjects will meet with the nutritionist at these same visits.

The subjects will maintain the behavior modification program worked out with the nutritionist and psychologist before surgery. These programs are individualized to each subject's dietary habits, eating habits, and quality of life issues. The subject will be encouraged and counseled to combine their Lap-Band tool with long-term modifications in their lifestyle, including exercise. Weight loss, status of pre-operative comorbidities and development of complications will be reviewed at every follow-up visit. This will include testing to follow pre-operative comorbidities. Baseline laboratory and nutritional parameters will be repeated every 3 months for the first year post op. OGTT will be performed at 1 year and 5 year on the subjects who have impaired glucose tolerance at baseline testing (excluding subjects who have type I or II diabetes who is not clinically safe to perform the test). However, if the HbA1c or fasting blood glucose tests show abnormal results or the subject develops polyuria or polydipsia, additional interval testing should be performed based on ADA guidelines.

All laboratory, gastrointestinal, EKG, nutritional, and psychiatric evaluations which were performed at baseline will be repeated every 12 months.

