3.7.7 Data Collection

Data will be collected by the principal investigator, the nurse practitioner, or nutritionist and documented on a standardized data form. The data will be entered by a research coordinator or the principal investigator in a fashion that maintains patient anonymity, using a unique identification number. The data will be entered into a secure computerized database, which can be accessed only by the principal investigator and the research coordinator with the use of a password. Data collection and statistical analysis will be performed by assigned research personnel, who will access the data using the unique patient identification number assigned.

We will collect relevant life history information from the subject's medical records including illnesses and hospitalizations that occur while subjects are participating in the research, as well as age, ethnic background, marital status, medical history, weight loss, changes in weight-related medical conditions, and information about the surgery and information about lap-band adjustments, and complications. We will collect medical information from physicians and other healthcare providers in General Surgery, Pediatric Surgery, Pediatrics, Psychiatry, and Psychology and from the NYU hospital medical records.

All data will be recorded on case report forms and compared at 6, 12, 24, 36, 48, and 60 months with baseline. Results will be reported descriptively as well as by modeling weight loss in order to assess aggregate outcomes and address the issues of safety and efficacy.

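### The primary % EWL model uses no weight before month 6, so implanted subjects lost early drop out of it; the estimate may be too high if they were losing weight poorly

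*Combined protocol and SAP*

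**What the plan says.** Section 3.7.6 (Statistical Methods) specifies a linear model for % EWL over "the covariance among repeated measures of weight loss from month 6 to month 60". On fitting, it states: "SAS PROC MIXED will be used in which two covariance structures will be examined by means of a REPEATED statement". These are unstructured (UN) and AR(1), chosen by AIC, with a random subject effect added under AR(1). Time is log-transformed. Baseline BMI enters as a covariate, not as a response.

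Section 3.4.5.1 (Scheduled Visits) states: "Study data will be collected at 1-2 week, 6 weeks, 3 months, 6 months, 9 months, 12 months, and every 6 months thereafter". It adds: "Subjects will be weighed and given a physical examination". Three post-operative weights are therefore scheduled before the model's window opens.

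Section 3.7.7 (Data Collection) also starts its comparisons at month 6: "All data will be recorded on case report forms and compared at 6, 12, 24, 36, 48, and 60 months with baseline".

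The secondary BMI model in 3.7.6 is built differently. There, baseline BMI "will be assigned a value of time 0 and will be included as an endpoint measure".

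Section 3.7 defines no analysis set, no rule for missing weights and no sensitivity analysis. Section 3.2.4 lets a subject or parent end participation whenever they wish, and lets the investigator discontinue a subject after three consecutive missed visits.

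**The concern.** PROC MIXED uses only records with a response. When the response starts at month 6 and baseline is only a covariate, a subject who was implanted but has no weight from month 6 on contributes nothing to the primary estimate. The plan does not ask for such subjects to be counted. The estimate then describes those still being weighed at month 6 or later, while the objective in 2.1 concerns the adolescents treated.

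A likelihood-based model could keep most of these subjects through weights already collected. If early departure depends on early weight loss, the week-6 and month-3 values carry the information needed to correct the later means. The sponsor's data-sharing attachment (Appendix 2, item 13) itself requests weights from 3 months for a pooled linear model, so the month-3 value is already treated as worth analysing.

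At stake is the size of the reported weight loss. In a single-arm study tested against zero, that size is the informative result.

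**Working it through.** The plan gives no expected early loss, standard deviation or sample-size derivation, so it has no figure to reproduce.

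**Inputs from the documents.** Up to 120 subjects (3.1). Mean 1-year % EWL in adults of 34.6% and 44.3% (1.1), used for illustration only.

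**Assumptions.** Loss before month 6 of d = 5%, 10% or 20%, which is 6, 12 or 24 of 120. Month-3 % EWL mean 18, SD 10; month-12 mean 34.6, SD 20; correlation 0.6. Dropout is logistic with a log-odds slope of 1 per SD.

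**Step 1: general formula.** The all-implanted mean is (1 − d) × retained mean + d × lost mean, so

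bias = d × (retained mean − lost mean).

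- Lost subjects 10 points worse: 0.05 × 10 = +0.5; 0.10 × 10 = +1.0; 0.20 × 10 = +2.0.
- Lost subjects 20 points worse: +1.0, +2.0, +4.0.
- No difference: 0.
- Lost subjects 10 points better: −0.5, −1.0, −2.0.

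**Step 2: does the month-3 weight repair it?** Simulation of 1,000,000 subjects under the assumptions above. Entries are bias in the month-12 mean, without the month-3 weight / with it by maximum likelihood.

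| Who leaves before month 6 | 5% lost | 10% lost | 20% lost |
|---|---|---|---|
| Unrelated to outcome | 0 / 0 | 0 / 0 | 0 / 0 |
| Poor losers at month 3 | +0.57 / 0 | +1.09 / 0 | +2.08 / 0 |
| Driven by later, unseen outcome | +0.95 / +0.62 | +1.81 / +1.19 | +3.47 / +2.31 |
| Good losers at month 3 | −0.57 / 0 | −1.09 / 0 | −2.08 / 0 |

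Dividing bias by d in the second row gives the implied gap between retained and lost: 0.57/0.05 = 11.4, 1.09/0.10 = 10.9 and 2.08/0.20 = 10.4 points. This agrees with the 10-point line of step 1. The calculation uses two visits rather than the planned log-time curve, so it shows order of magnitude only.

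**Step 3: scale.** With SD 20 to 30, the standard error of a mean in 120 subjects is 20/√120 = 1.8 to 30/√120 = 2.7. The second-row bias is below one standard error at 5-10% loss and close to one at 20%.

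**Step 4: covariance.** The repair needs the slope of month 12 on month 3, which is 0.6 × 20/10 = 1.2 here. A model with equal variance at every visit, which includes AR(1) with a random subject effect, forces that slope to equal the correlation and so to be at most 1. At a correlation of 0.6 it would apply 0.6/1.2, about half of the correction. Variance must be allowed to differ by visit.

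**Step 5: extreme case, all lost subjects at 0% EWL.** Multiply the retained mean by (1 − d): 34.6 becomes 32.9, 31.1 or 27.7, and 44.3 becomes 42.1, 39.9 or 35.4, at 5%, 10% and 20% loss.

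**Step 6: the test against zero.** With 20% lost and set to 0,

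z = 34.6 × 0.8 / (√(SD² × 0.8 + 34.6² × 0.2 × 0.8) / √120).

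For SD 20: 27.68 / (√511.5/√120) = 13.4. For SD 30: 27.68 / (√911.5/√120) = 10.0.

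**Step 7: covariance parameters.** Months 6, 9, 12, 18, 24, 30, 36, 42, 48, 54 and 60 are 11 visits, so UN has 11 × 12/2 = 66 parameters. With week 6 and month 3, it has 13 × 14/2 = 91.

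**The case against.** A reader might infer that the month-6 start simply overstates weight loss. The documents do not support that. They give no early-loss rate and nothing on how early leavers fare, and section 3.4.5.2 foresees weight being lost both too fast and too slowly. Step 1 shows the bias can be positive, zero or negative. This objection stands.

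The hypothesis is only that % EWL exceeds zero, and step 6 shows this is safe. This also stands, and limits the point to estimation.

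Loss may be rare. Section 3.2.4 provides for telephone calls, registered letters and offered transport when a subject withdraws, and no section says band removal ends follow-up. Explantation should therefore not be equated with lost data.

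The remedy is partial. Where loss depends on an outcome not yet seen, more than half of the bias remains in step 2. A subject removed for missing all three early visits has no scheduled early weight to restore.

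Two further inferences carry little weight. The BMI model keeps subjects with baseline only, so the two endpoints can rest on different people; but % EWL is zero at baseline by definition, and adding early visits does not remove the difference. The model also skips much of the fast initial phase, but 3.7.6 says the shape of the curve is not part of the hypothesis, and early visits entered as separate levels would not change the fitted month 6-60 curve's scope.

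What survives is that the stated window excludes subjects for whom relevant weights may exist, and the plan neither justifies nor counts the exclusion.

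**Conclusion.** The point holds as a conditional one. The primary model leaves out any implanted subject with no weight from month 6 on, although three earlier weights are scheduled. If early loss is related to poor early weight loss, the month-12 % EWL would be overstated by roughly 0.5 to 1 point at 5-10% loss and about 2 points at 20%. It is unbiased if loss is unrelated to outcome, and understated by similar amounts if good losers leave. The loss rates, SDs, month-3 mean, correlation and dropout slope are all assumed, and the 34.6% is an adult figure. The conclusion that % EWL exceeds zero is not threatened. The change is still worth making, because it is cheap and bears on the number that will be quoted.

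**What to change.** In 3.7.6:

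- Add the week-6 and month-3 % EWL values to the response vector as separate visit levels, so that they inform the later means without bending the month 6-60 trend.
- Use a covariance that lets variance differ by visit: UN, or heterogeneous AR(1) if UN does not converge.
- Define the primary set as all implanted subjects with any post-operative weight. A subject whose only weight is from week 1-2 still has no response in this model and should be counted openly.
- Report means for months 6-60 as now, together with the number of implanted subjects who have no weight from month 6 on.
- Add a sensitivity analysis setting those subjects to 0% EWL. It is needed because early weights do not remove bias from loss that depends on later unseen outcome, and cannot restore someone who missed every early visit.

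The cost is analysis wording only, since the weights are already scheduled. Under UN, the covariance parameters rise from 66 to 91 with at most 120 subjects, which brings some convergence risk; hence the named fallback. The estimate may also become slightly less favourable.

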3.0 INVESTIGATIONAL PLAN

3.1 Study Design

This is a prospective, non-randomized, single-center study to be conducted under an FDA-approved Investigational Device Exemption (IDE). One investigational site will enroll and treat up to 120 subjects who meet the criteria for use of the LAP-BAND® System, except that they are adolescents ages 14 to 17. Subjects will be followed for five years.

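### The % EWL covariance rule (UN, or AR(1) plus a subject effect) has no random slope or stated small-sample correction, so reported precision can be optimistic

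*Combined protocol and SAP*

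**What the plan says.** Section 3.7.6 plans a linear model in which the "covariance among repeated measures of weight loss from month 6 to month 60 is" modeled, using SAS PROC MIXED. On the choice of structure, "two covariance structures will be examined by means of a REPEATED statement: unstructured (UN) and autoregressive (AR(1". Then "AIC will be examined to determine the most suitable structure", and "In the case that AR(1) is selected, a RANDOM statement for Subject will be included in the model". The mean model uses baseline BMI and log time: "To test for this decelerating trend, Time will be log transformed". The structure chosen for % EWL is carried over to BMI.

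Section 3.7.6 names no random slope, continuous-time structure, robust standard error or degrees-of-freedom method. Its residual check concerns the mean time course, not the covariance.

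On visits, section 3.4.5.1 states: "Study data will be collected at 1-2 week, 6 weeks, 3 months, 6 months, 9 months, 12 months, and every 6 months thereafter". Section 3.7.7 gives a shorter list, with data "compared at 6, 12, 24, 36, 48, and 60 months with baseline". On size, section 3.1 states: "One investigational site will enroll and treat up to 120 subjects".

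**The concern.** Each permitted branch has a weakness. UN fits any pattern of variances and correlations, but it estimates many parameters from a modest sample, and model-based standard errors ignore the error in those estimates. AR(1) with a subject intercept is economical, but it holds the variance constant and gives every subject the same slope on log time. Band adjustment is individual (section 3.4.5.2), so subjects may well lose weight at different rates. If they do, that variation is missing from the standard error of the time effect.

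The order of steps is a further problem. Read literally, AIC compares AR(1) without the subject effect, and the effect is added only after AR(1) has won. The AR(1) model reported would then not be one that AIC compared.

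At stake is the stated precision of the five-year % EWL estimates, the time trend and BMI. In a one-arm trial tested against zero, the estimates and their uncertainty are the informative result.

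**Working it through.** **Inputs.** Section 3.4.5.1 gives visits in the modelled window at months 6, 9, 12, 18, 24, 30, 36, 42, 48, 54 and 60: 11 visits, with gaps of 3, 3, then 6 months. Section 3.7.7 gives six. Section 3.1 gives n up to 120. The documents give no SD, correlation, slope variance, dropout rate or coverage figure, so there is no plan figure to reproduce.

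**1. UN parameters.** p(p+1)/2 gives 11 × 12/2 = 66 for 11 visits and 6 × 7/2 = 21 for six.

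**2. UN, uncorrected.** With complete data, a mean linear in log time and REML, put ν = n − 2 and k = p − 2. Relative to the variance with a known covariance, the estimated variance averages (ν − k)/ν and the true variance is (ν − 1)/(ν − k − 1). Hence

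reported SE / true SE = √[(ν − k)(ν − k − 1) / (ν(ν − 1))].

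For n = 120 and p = 11, ν = 118 and k = 9: √[(109 × 108)/(118 × 117)] = √(11772/13806) = 0.923. Coverage is 2Φ(1.96 × 0.923) − 1 = 93.0%. No SD or correlation is needed.

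| Complete subjects | 11 visits: SE too small by | Coverage | 6 visits: SE too small by | Coverage |
|---|---|---|---|---|
| 120 | 7.7% | 93.0% | 3.4% | 94.2% |
| 100 | 9.2% | 92.5% | 4.1% | 94.0% |
| 80 | 11.6% | 91.7% | 5.2% | 93.7% |
| 60 | 15.7% | 90.2% | 7.0% | 93.2% |

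The lower rows apply to that many complete subjects, not to 120 with some dropout. Simulated UN with 120 enrolled and 11 visits, with 0% or 30% monotone dropout, covered 92.8-94.2%.

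**3. AR(1) plus random intercept.** This step needs assumptions. With intercept SD 15 points, serial correlation 0.7 per 6 months and subject slope SD 4-8 points per log-month, the log-time slope SE was roughly 5-25% too small in most cases, and up to 41% when the serial SD was small. In coverage, 5% too small means 2Φ(1.96 × 0.95) − 1 = 93.7%, and 25% means 2Φ(1.96 × 0.75) − 1 = 85.8%.

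A separate simulation used N = 120, 11 visits, 0% or 30% dropout and 1,000 runs per case (Monte Carlo error about 0.7 points). Assumed total SD was about 14-22 in most cases, rising to about 29 at month 60 with large slopes. This branch covered:
- with no random slopes, 94.3-96.6%, including truths where correlation decays in calendar time, so unequal spacing alone costs almost nothing;
- with moderate slopes, 90.3-92.5% for the month-60 mean and the slope;
- with large slopes, 85.9-86.8% for the same two targets;
- at month 6 with random slopes, about 99-100%, so the error is not always in the narrow direction.

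**4. The AIC rule as a whole (same simulation).** Coverage was 93.5-96.5% without random slopes. With large slopes it was 93.0-94.2%, and UN was chosen in every run. With moderate slopes it was 91.9-95.2%, and UN was chosen in 66-86% of runs. The order of steps can change the choice: with a random intercept plus continuous-time decay and no dropout, UN won 55.3% of runs when AR(1) was compared without the subject effect and 2.9% when compared with it.

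**5. Test against zero.** Assume a mean of 35-45% EWL and SD 20. The SE is 20/√120 = 1.83, so z is 35/1.83 = 19 to 45/1.83 = 25. Multiplying the smaller value by the worst UN ratio in the table gives 19 × 0.843 = 16. Rejection does not change.

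**The case against.** The plan's hypothesis is that % EWL is positive, and section 3.7.6 places the shape of the time course outside that hypothesis. Step 5 shows that the test is safe. The plan also specifies no 95% interval for % EWL, so coverage here only expresses how far the standard errors are off. Both points stand, and they limit the matter to reported precision.

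The lack of a correction is inferred from silence: Kenward-Roger is not excluded. That is true, but an analyst following the text would have no instruction to request it.

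The model might use only the six times in section 3.7.7, which shrinks the UN problem to about 3% at 120. That also stands as a possible reading, although section 3.7.6 does not restrict the visits between months 6 and 60.

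The sentence on the RANDOM statement could mean that the AR(1) candidate carries the subject effect when AIC is computed. The wording allows this, so the plan should say which is meant.

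A reader might infer more: that unequal visit gaps invalidate AR(1), that AIC will usually keep AR(1), or that intervals cover only 91-93% whichever branch is chosen. The documents support none of these. Spacing alone costs almost nothing. How often AIC keeps AR(1) depends on serial SD, measurement error and intercept centring, none of which the documents give: varying them moved the rate from 0% to 88% at slope SD 4. Without random slopes, AR(1) plus intercept covers about 95%.

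**Conclusion.** The point holds as a weakness in how precision will be reported, not as a threat to the primary conclusion. The firmest part is UN: over 11 visits without correction, standard errors are about 8% too small at 120 complete subjects, 12% at 80 and 16% at 60, with no assumption about variances. This requires that all 11 visits are modelled and that no correction is applied.

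The AR(1) part is conditional on subjects differing in their log-time slopes. If they do, the time-effect standard error is too small, by roughly 5-25% in most assumed cases. Month-60 coverage then ranges from nominal to about 90% or lower, depending on slope size and intercept centring. The change is worth making because it is cheap and BMI inherits the chosen structure.

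**What to change.** In section 3.7.6:

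1. Specify DDFM=KR (Kenward-Roger) for all tests and intervals, including under UN.
2. Replace the AR(1) candidate with a random intercept and random log(month) slope by subject (TYPE=UN), plus REPEATED with TYPE=SP(POW)(month). A model of this type, even without Kenward-Roger, covered 94.6-96.2% in three assumed truths with 30% dropout (500 runs each).
3. Compare AIC only between models in the form in which they will be reported.
4. State whether the model uses all 11 visits or the six in section 3.7.7.
5. Give BMI its own stated time scale. Its baseline enters at time 0, where log(month) is undefined, so the random slope cannot be carried over unchanged.

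The cost is a few lines of SAS and SAP wording and slightly wider intervals. No new data are needed.

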3.2 Study Population

3.2.1 Inclusion Criteria

1. Be at least 14 and less than 18 years of age at the time of enrollment into the study, at Tanner developmental stage 4 or greater, and be past the point of peak height velocity. Bone age will be determined in this evaluation.
2. Have a BMI of at least 40 [BMI is calculated as follows: $BMI = \text{weight (Kg)} / (\text{height (m)}^2)$; i.e. (W/H²) or Kg/m²]. These criteria are the ones recommended by the NIH for adults. When applied to adolescents, they are more conservative than the criteria of BMI > 95th percentile for age because of the BMI curves for children and adolescents. We feel the criteria proposed in Pediatrics, 2004;114(1):217-223 are unnecessarily restrictive given the incidence of comorbidities starting at a BMI of 35, the likelihood of the development of comorbidities starting at a BMI of 35, and the poor results of therapies which do not include bariatric surgery for adolescents with a BMI of 35 or greater.
3. Have a history of obesity for at least 5 years, including failed attempts at diet and medical management of obesity.
4. Express willingness to follow protocol requirements which include signing an assent form, having the individual's legal guardian sign a consent form; completing 1-2 week, 6 week, 3 month, 6 month, 9 month, 12 month, and every 6 month follow-up visits for a total of five years, and completing all protocol-required laboratory and diagnostic tests.
5. Confirmation by a psychologist or psychiatrist experienced with adolescents that the subject is sufficiently mature emotionally to comply with the study protocol.

6. Assure investigators that subject, if female of childbearing potential, is using an appropriate form of contraception.

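### Does the plan need to name the model contrast, the month and the sidedness that test % EWL against zero?

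*Combined protocol and SAP*

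**What the plan says.** Section 3.7.6 fits a repeated-measures mixed model to % EWL from month 6 to month 60, with log-transformed time and baseline BMI as a covariate. It singles out time as the predictor of most interest and says: "To test for this decelerating trend, Time will be log transformed".

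The hypotheses concern level: "The null hypothesis is that % EWL will remain unchanged (i.e., at zero) post surgery", against "The alternate hypothesis is that % EWL will be positive post surgery". On error rate it says only: "An alpha of 0.05 will be used to determine if the null hypothesis is rejected". It then takes the trend out of the hypothesis: "The form of the weight loss over time is not part of the hypothesis of the study".

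Sections 3.7.1 and the Protocol Summary define the primary variable as % EWL and give no time point. Section 3.7.7 says that all data will be "compared at 6, 12, 24, 36, 48, and 60 months with baseline", with both descriptive and model-based reporting. None of those six months is ranked first.

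**The concern.** The null is about a level, but the only model term that 3.7.6 links to a test is log time, which is a slope. No least-squares mean, average or other contrast is tied to the null. The alternative has a direction, but the tail convention for alpha is not stated.

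Two things could then go wrong. First, someone might read the test off the wrong coefficient. A slope can be zero while weight loss is large and sustained. The raw intercept refers to a BMI of zero, although section 3.2.1 requires subjects to "Have a BMI of at least 40". Second, because a test against zero is almost certain to succeed, the informative result is the estimate and its confidence interval, and the plan does not say which month supplies the headline figure. Section 1.1 quotes different means at 1, 2 and 3 years, so the choice would matter to a reader making comparisons.

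**Working it through.** The plan gives no power, target effect or SD, so there is no figure of its own to reproduce. The check asks whether the unstated choices change the decision, and how far they move the estimate.

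**Inputs from the document:** up to 120 subjects (3.1); mean % EWL of 34.6 at 1 year and 38.2 at 2 years in the US adult study (1.1); alpha 0.05; the model window and terms (3.7.6).

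**Assumed:** SD of % EWL 15, 25 or 40 points; 120, 60, 30 or 15 subjects with data. For the model: 11 visits from month 6 to 60, a random subject effect carrying half the variance, AR(1) correlation 0.5, and baseline BMI with mean 47 and SD 6.

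**1. Decision, one-sample form.** With noncentrality μ√n/σ, power is the probability that a noncentral t on n − 1 degrees of freedom exceeds its critical value. For μ = 34.6 (one-sided / two-sided):

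| SD | n = 120 | n = 60 | n = 30 | n = 15 |
|---|---|---|---|---|
| 15 | >0.999 / >0.999 | >0.999 / >0.999 | >0.999 / >0.999 | >0.999 / >0.999 |
| 25 | >0.999 / >0.999 | >0.999 / >0.999 | >0.999 / >0.999 | 0.9997 / 0.9987 |
| 40 | >0.999 / >0.999 | >0.999 / >0.999 | 0.9986 / 0.9956 | 0.938 / 0.876 |

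**2. Decision, planned model.** A log-time line through the two US means has slope (38.2 − 34.6)/ln 2 = 5.19. This gives 34.6 − 5.19 × ln 2 = 31.0 at month 6 and 34.6 + 5.19 × ln 5 = 43.0 at month 60. With n = 120 and SD 40, the standard error of the level at mean BMI is 3.46 at month 6 and 3.15 at month 60. The ratios to zero are 31.0/3.46 = 9.0 and 43.0/3.15 = 13.7. With n = 30 and SD 40, month 6 gives 31.0/6.92 = 4.48, so two-sided power is Φ(4.48 − 1.96) = 0.994. The decision is the same at either end of the window.

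**3. Sidedness.** The smallest observed mean that rejects is t × SD/√n. At n = 120 it is 2.27 (one-sided) or 2.71 (two-sided) for SD 15, and 6.05 or 7.23 for SD 40. The differences are 0.44 and 1.18 points. At n = 60 and SD 40, the two conventions disagree only for an observed mean between 8.63 and 10.33.

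**4. Which estimate.** On the same illustrative line, the six months in 3.7.7 give 31.0, 34.6, 38.2, 40.3, 41.8 and 43.0, and the average over the 11 visits is 38.3. The spread is 43.0 − 31.0 = 12.0 points. For comparison, the two-sided 95% half-width of a single-visit mean at n = 120 is 2.71 to 7.23 points.

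**5. The wrong coefficients.** If % EWL is flat after month 6, a log-time slope test finds a positive slope with probability 0.025 (two-sided) or 0.05 (one-sided), however large the sustained loss. With time in months, BMI uncentred and no BMI effect, the raw intercept has a standard error of 10.2 to 27.1 at n = 120 and rejects with probability 0.57 down to 0.12 (two-sided). Neither is a level within the data window. Section 3.7.6 itself rules out the slope by excluding the form over time from the hypothesis. The intercept's meaning depends on coding that the plan does not state: with time in years, log time is zero at month 12.

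**The case for a change.** The strongest case for a change is that the fix is cheap and the month matters. One sentence and one estimate statement would settle it. The spread across months in step 4 exceeds the confidence half-width at every SD considered. The plan also had opportunities to settle the month. Section 3.5 schedules an early effectiveness look at the first 10 patients at 6 months, the data-sharing attachment says the site had already published short-term efficacy, and the text dated July 2013 (Amendment 10) still names no month. A reader cannot exclude a headline month picked after the fact.

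What stands is that naming the contrast would be tidier. The rest carries little weight. Picking a favourable month would mean departing from 3.7.7, which sets comparisons at all six. Even then, if the true level were flat, reporting the highest of the six would overstate it by an average of 0.9 to 1.6 points (simulated with 120 complete subjects, between/within SDs of 18/9, 15/12 or 20/15, and AR(1) correlation 0.6). Nothing in the document shows that 3.7.6 was shaped by interim or published results, and the plan sets no formal comparison with the 1.1 benchmarks. A fitted curve with intervals at fixed months is a legitimate primary summary for a single-arm study. Variation of % EWL with time is what the model is there to estimate, so several estimates do not amount to an ambiguous one.

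**Conclusion.** The omission is genuine but is only missing detail. The stated null, the directional alternative and the exclusion of trend together point an analyst to an adjusted mean % EWL within months 6 to 60. At the cited effect sizes, every such contrast rejects zero with probability above 0.999 at 120 or 60 subjects and at least 0.99 at 30, on either tail convention. Choices of month and sidedness could change the decision only if the true mean were far below the cited 34.6%, or if very few subjects had data (15 with SD 40: 0.88 to 0.94). The estimate does depend on the month, but the plan already commits to six fixed months.

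This rests on an assumed SD of 15 to 40 points and on adult means carried over to adolescents. The 12-point spread is illustrative only: the two US means come from 221 and 122 subjects, and the values at month 6 and beyond month 24 are extrapolated. Smaller n represents loss of numbers, not selective dropout, which naming a contrast would not cure. No change to the plan follows.
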